Chronic disease models also allow health systems to reach out to all smokers, not just those who are seeking treatment and ready to quit. In the US, 80% of smokers are “not ready to quit” in the next 30 days.⁴⁸ From a public health standpoint, an effective intervention for this group may have an even greater impact than programs targeting the minority of smokers who are ready to quit.⁴⁹ Furthermore, few evidence-based treatments are available to help “not ready to quit” smokers.^{21,50,51}

b. Preliminary work supporting the proposed study

In prior work, I developed a text message program called the getReady2Quit program (R2Q) and pilot-tested its feasibility among CHC patients. We recruited smokers at MGH Revere and Charlestown using a proactive recruitment process which consisted of sending a letter from the subject’s PCP notifying them of the study, followed by a single text message invitation to opt-in to R2Q. Among 1,603 smokers, 1,279 (80%) had a mobile number in the EHR and 949 were approved by their PCP for the study. 9% (88 of 949) of smokers opted in to R2Q following the letter and single recruitment text and this included both ready to quit (68%) and not ready to quit smokers (32%). The R2Q pilot model had two components. Part 1 targeted smokers who were ready to quit in the next 30 days by proactively recruiting them to a text message program with content to support them through a quit attempt. Part 2 targeted smokers who were not ready to quit. They were sent novel motivational messages and advice to try a ‘Practice Quit Attempt’. This work demonstrated the feasibility of delivering a text messaging program to primary care patients. Subjects in the feasibility study are being recruited to participate in qualitative interviews to further improve the program design and content prior to the current trial.

c. Study rationale

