This will be a 4 arm randomized controlled trial among 206 smokers who are patients at Massachusetts General Hospital and who receive primary care from a Partners primary care provider. Patients will be proactively recruited from MGH primary care practices. Patients will also be recruited from online advertisements on the Partners Clinical Trials website, from among MGH primary care patients who consent to participate in Research Offers Direct to You, and by referral from the MGH inpatient Tobacco Treatment Service counselors. We will recruit both smokers who are ready to quit smoking in the next 30 days and those who are not planning to quit in the next 30 days. The text message program is tailored to readiness to quit. For those ready to quit in the next 30 days, they will be sent messages based on the SmokeFreeTXT content. For those not ready to quit, we have developed content including motivational advice and tips to try a practice quit attempt for a few hours or days.⁵³ The text message program will also include medication adherence support text messages based on the Information-Motivation-Behavioral Skills model of adherence.⁵⁴ Combination NRT is first-line therapy which is more effective than nicotine patch alone and will be offered to daily smokers, dosed per package instructions.²¹ Smokers who are not ready to quit and who are randomized to one of the two nicotine medication arms will be offered one box of lozenges to try in a practice quit attempt.⁵³

The RC will not be blinded to treatment assignment because he/she will register subjects randomized to the text messaging arms in the text messaging program during the enrollment telephone call to verify receipt of an enrollment confirmation text message ("Hi [First name] Welcome to getReady2Quit (R2Q). Your messages and ratings will start soon. Reply STOP to quit, HELP for info. Msg&DataRatesMayApply"). Randomization will be done by a computer generated random sequence.

b. Procedures for obtaining informed consent (including timing of consent process)

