ADHERENCE: length of active time in the text messaging program. At least twice per week a text message will be followed by another text message asking respondents if they found the message useful. Active time will be defined as number of days from enrollment to last reply to these usefulness messages.

ENGAGEMENT: number of messages sent from participant to the server. Messages from the participant could be in response to the periodic questions about how they are feeling or to request specific help with cravings, mood symptoms, or slips. We will exclude responses to the receipt confirmation messages from this total.

COMPLAINTS: due to technical issues or programmatic issues received by the technical helpline.

e. **Remuneration**

We will pay subjects \$0.25 per text message sent or received from the program server up to \$50 or 200 text messages. Participants will be issued \$20 for completion of the baseline survey and \$10 for follow-up surveys at 1, 2 and 6 weeks after enrollment. Participants will be issued another \$40 after completion of the outcome telephone interview. Participants will be issued \$20 if they complete a CO measurement. A small subset of participants will be issued a \$10 gift card for a qualitative exit interview. All payments for surveys and for the CO measurement will be issued by a gift card. Text message reimbursement will be issued by check every 4 weeks.

VI. BIOSTATISTICAL ANALYSIS

At the start of the project, MGH Primary Care Practice Based Research Network staff will identify the target population of documented smokers in MGH primary care practices and create a database that includes baseline variables from the EHR. We will use REDCap to collect baseline self-reported data and outcomes. At the end of the study we will merge the EHR data from the Primary Care Practice Based Research Network, REDCap, and MobileCommons for analysis (see Data Collection sheets).

Data analysis

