The sample of smokers enrolled in the study will be characterized on baseline measures from the EHR and compared to the population of smokers whom we attempted to contact in order to determine the sample's representativeness to the target population. Variables include demographics, medical history, and practice characteristics. We will also compare baseline characteristics collected from the EHR and from baseline interviews between the 4 randomized groups to determine the success of randomization. The primary outcome analysis will be conducted as intention-to-treat, comparing the primary outcome using chi-square analysis or multiple logistic regression analysis if any baseline factor is significantly imbalanced by group ($p<0.05$) as independent variables. The 4 arm design allows for analysis as a factorial design. We will first test for interaction between the NRT and TM interventions and if no interaction is detected we will test the effect of text messaging using both TM and TM+NRT arms compared to BA and NRT arms. If interaction is present, we will compare the TM arm to BA for our primary analysis. We will secondarily compare the groups in terms of self reported 7 day PPA, biochemically confirmed abstinence, number of days not smoked, use of ≥ 1 evidence based treatments, and cigarettes per day using chi-square or t-tests or logistic or linear regression if groups are imbalanced. We will also compare the TM+NRT group with the NRT group in terms of total days of medication used and total mg of medication used over 2 weeks using linear regression. We will conduct stratified analyses of the primary outcome, 7 day PPA, treatment use and days not smoked by readiness to quit in the next 30 days.

Sample size

Hypothesis 1: A 12 week text messaging intervention (up to 30 days pre-quit through 8 weeks post-quit) providing behavioral support will increase the proportion of smokers making a quit attempt compared to a control group receiving brief advice.

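### Representativeness to the target population is judged only against the smokers the study tried to reach, so selection before contact, chiefly removal by the PCP, cannot show up in the check

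*Combined protocol and SAP*

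**What the plan says.** The opening paragraph of section VI (Biostatistical Analysis) says that the research network staff "will identify the target population of documented smokers in MGH primary care practices" and will "create a database that includes baseline variables from the EHR". The target is therefore defined, and EHR data on it are planned.

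The Data analysis paragraph then says that enrollees will be "compared to the population of smokers whom we attempted to contact", and that this is done "in order to determine the sample's representativeness to the target population". On content it adds: "Variables include demographics, medical history, and practice characteristics". No other section adds a comparison with the whole target or splits this one by recruitment route.

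Two filters act before contact. PCPs review the list and remove patients they do not want approached (section III opening text, III.a and IV.b). A mobile number in the EHR is an inclusion criterion (section III). The pilot gives their scale: "1,279 (80%) had a mobile number in the EHR and 949 were approved by their PCP for the study", out of 1,603 smokers (section I.b).

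Recruits come by four routes (III.a and IV.a): PCP-approved outreach, the RODY research-contact programme, a website advertisement, and "by referral from the MGH inpatient Tobacco Treatment Service counselors". For website respondents, section III waives the requirement for an MGH PCP; a PCP elsewhere in Partners and an MGH record number suffice.

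**The concern.** The comparator and the stated purpose do not match. A comparison with contacted smokers shows what happened between contact and enrolment: opt-out, failure to reach, refusal. It says nothing about how contacted smokers differ from the smokers removed first. Removal by a PCP could plausibly depend on the characteristics being compared, such as medical history and practice. If it does, the sample can look just like its comparator and still differ from the population it is meant to represent.

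This matters because the background section presents the trial as filling a gap about the broad population of primary care smokers, and the Sample size section names recruitment rates among the quantities the pilot is meant to estimate. False reassurance on reach would carry into the planning of later studies.

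A second, smaller issue is that the enrolled sample is treated as one group although its routes differ. Website respondents with a Partners PCP outside MGH are not in the target as section VI defines it. Inpatient referrals have been pre-selected by counsellors.

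**Working it through.** **Inputs.** From the pilot in section I.b: 1,603 smokers identified, 1,279 with a mobile number, 949 PCP-approved, 88 opted in. I read the 949 as a subset of the 1,279, since the pilot invitation went by text. The gaps between contactable and removed smokers are my assumptions; the documents give none.

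**Reproducing the stated figures.** 1,279/1,603 = 79.8% (stated 80%). 88/949 = 9.3% (stated 9%). Both agree.

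**Share removed before contact.**
- No mobile number: 1,603 − 1,279 = 324.
- Mobile number but not PCP-approved: 1,279 − 949 = 330, which is 330/1,279 = 25.8%.
- Both together: 324 + 330 = 654, which is 654/1,603 = 40.8%.

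The first share takes the target as smokers who could receive the programme. The second takes section VI literally, since its definition has no telephone condition.

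**Difference the check cannot see.** Let r be the share removed, p_c the prevalence of a characteristic among contactable smokers and p_r its prevalence among removed smokers.

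Target prevalence = (1 − r) × p_c + r × p_r

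If the sample matches the contacted group exactly, the planned check shows p_c − p_c = 0. The true difference from the target is

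p_c − target prevalence = r × (p_c − p_r)

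| Assumed gap p_c − p_r (points) | r = 25.8% | r = 40.8% | Planned check |
|---|---|---|---|
| 5 | 1.3 | 2.0 | 0 |
| 10 | 2.6 | 4.1 | 0 |
| 20 | 5.2 | 8.2 | 0 |
| 30 | 7.7 | 12.2 | 0 |

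One row in full, with assumed prevalences of 50% and 30%. At r = 25.8%, the target is 0.742 × 50 + 0.258 × 30 = 44.8%, a difference of 5.2 points. At r = 40.8%, it is 0.592 × 50 + 0.408 × 30 = 41.8%, a difference of 8.2 points.

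**Recruits from outside the target.** If they form a share w of the sample and differ from the rest by d points, they shift the sample by w × d. For assumed w of 5% to 30% and d of 10 to 40 points, that runs from 0.05 × 10 = 0.5 to 0.30 × 40 = 12 points. The documents give no counts by route, so w is unknown and may be small.

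**Denominators.** Pilot uptake is 88/949 = 9.3% of approved smokers and 88/1,603 = 5.5% of all identified smokers. Both are legitimate, but they answer different questions, so a reported rate needs its denominator stated.

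**The case against.** The best defence has several parts.

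- **The planned check is not empty.** It covers the largest pilot loss: 949 − 88 = 861 of 949 (91%) approved smokers did not opt in. That stands, and is why the comparison should be kept.
- **Half of the 654 were not eligible.** The 324 smokers without a mobile number fail an inclusion criterion and could not receive the programme. Section III also applies a telephone criterion when the cohort is drawn. It would therefore be wrong to read the whole 41% as hidden selection among eligible smokers. The 26% removed at PCP approval remains, although PCP review itself partly screens for eligibility (IV.b).
- **The pilot may not transfer.** It ran at two health centres with a letter and a single text; the trial uses repeated telephone calls. The removal share is therefore an assumption, as is any gap.

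A reader might infer more than the text supports on two points. The first is that website and inpatient-service recruits all lie outside both the target and the contacted group. They do not necessarily: section III says that both are contacted by the study, and either route can yield MGH primary care smokers. Only website respondents with a non-MGH PCP are clearly outside the target. If they count as contacted, the comparator itself holds people from outside the target, and the mismatch remains. The second is that the recruitment rate will be wrong. The plan defines no pooled rate, and the Sample size section speaks of proactive outreach.

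**Conclusion.** The point holds. Section VI names one population and checks against a narrower one, and no other section repairs this. Removal by the PCP before contact is invisible to the check. If the trial's removal shares resemble the pilot's, the unseen difference is 1.3 to 7.7 points with 26% removed, or 2.0 to 12.2 points with 41% removed, over assumed gaps of 5 to 30 points.

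The documents do not show that any such gap exists, so it cannot be said that the sample will be unrepresentative, only that this check could not tell. Nor does the plan set a pass/fail threshold. The enrolled sample may, rather than will, include people from outside the target.

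The effect is confined to what the trial can say about representativeness and reach. The randomised comparison, the power statements and the sample size are untouched. The change is still worth making, because it is nearly free and alters a conclusion that the plan says it will draw.

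**What to change.** In section VI, Data analysis:

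1. Compare participants recruited through practice-network outreach or RODY with all documented smokers in the EHR database planned at the start of that section.
2. Keep the comparison with contacted smokers as a second step, described as a check on selection after contact.
3. Tabulate the same EHR variables at each step the database holds: listed, PCP-approved, contacted, enrolled.
4. Describe website and inpatient-service recruits separately, with counts by route.
5. Report the recruitment rate for outreach recruits, with its denominator stated.

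The cost is a change of wording and a little more tabulation, since the database is already planned. One limit applies: section III uses a telephone criterion when drawing the cohort, so a row for smokers without a telephone number is possible only if the extract holds them. If it does not, the plan should say that the target is restricted to smokers with a listed number.

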Rationale: In order to test the effect of text messaging on medication adherence, we need to have treatment groups receiving medication and medication plus text messaging. To deliver medication, mailed NRT, like text messaging, reaches patients outside of the busy office visit. Mailed NRT alone has also been shown to increase cessation⁵⁵ and may itself be an effective intervention compared to standard care.

3. Text messaging (TM): Brief advice + 12 week personalized, tailored text messaging program.

Rationale: Text messaging shows promise as an intervention to help smokers to quit.^{8,56} However, it has not been well tested among primary care patients. Text messaging may connect those primary care smokers who do not access currently available treatment services like telephone counseling or prescribed medication with assistance outside of the clinic office.

4. Text messaging and nicotine replacement therapy (TM+NRT): Brief advice + 12 week personalized, tailored text messaging program + 2 weeks of nicotine patches and/or lozenges mailed to subject.

Rationale: As above, in order to test the effect of text messaging on medication adherence, we need to have treatment groups receiving medication and medication plus text messaging. Text messaging has been shown to increase medication adherence in other conditions³⁴⁻³⁷ and medication adherence is suboptimal among users of smoking cessation medications.^{38,39,41} Integrating text messaging within healthcare systems offers opportunities to coordinate with pharmacotherapy and this 4 group design allows us to test the effect of text messaging alone on smoking outcomes and the effect of text messaging on NRT use.

We will use stratified block randomization. We will stratify by practice and readiness to quit in the next 30 days. We will use variable block sizes. Subjects will be randomized 1:1:1:1.

After verbal consent and chart review by the PCP. Randomized enrollees will be asked to complete a baseline telephone survey. After completion of the baseline survey, participants will be mailed a \$20 gift card.

Following the telephone survey, smokers randomized to the text messaging arms (TM and TM+NRT) will have their mobile numbers, and first names entered into the MobileCommons web-based platform. The program will be tailored to readiness to quit and user-entered quit date and personalized with individual's first name.

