We will attempt to obtain exhaled carbon monoxide samples from study participants who self-report 7 day point prevalent abstinence at end of treatment using the coVita | Bedfont Micro+ Smokerlyzer carbon monoxide monitor. The device will be used, maintained, and calibrated in accordance with the manufacturer's instructions.

Subjects randomized to the TM and TM + NRT arms will have their mobile telephone number, first name and PCP's name entered into the MobileCommons web-based text messaging platform. Their name will be used to personalize text messages.

d. Study visits and parameters to be measured

This study will be primarily conducted by telephone contact, email if the participant chooses, and mailings with a single in-person contact for subjects reporting abstinence from smoking at the end of treatment to collect an exhaled carbon monoxide sample to confirm abstinence. Subjects will be contacted by telephone and data collected by self-report at time of enrollment (baseline assessment interview), and by telephone or email for 1, 2, and 6 weeks after enrollment (follow-up outcome assessments), and end of treatment (primary outcome).

We will also offer a qualitative exit interview to be completed by phone for 10 participants per intervention arm (TM, TM+NRT, and NRT).

Baseline assessment:

Variables obtained from the EHR:

- Demographic factors: age, sex, health insurance (commercial, Medicare, Medicaid, no insurance or other), name, and address
- Medical history: coronary heart disease, COPD, diabetes, hypertension, cancer
- Practice characteristics: PCP, practice, number of visits to practice in past year

Variables obtained from baseline telephone interview:

- Smoking patterns: daily or non-daily, years smoked, Fagerstrom test for nicotine dependence (includes time to first cigarette after waking and cigarettes smoked per day)⁶⁴, number of previous quit attempts defined as any serious quit attempt lasting ≥ 24 hours ⁶⁵ ever and in the last 12 months, during the past 30 days, on how many days did you have at least one cigarette, and do you ever use menthol cigarettes.
- Demographic factors: ethnicity, race (white, black, Native American, Asian, Native Hawaiian or other Pacific Islander, other, unknown), and education
- Any prior use of smoking cessation medication (nicotine patch, lozenge, gum, inhaler or nasal spray, varenicline, or bupropion)

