The sample size for this pilot study is selected to adequately estimate recruitment rates, retention, and to get a preliminary estimate of prevalence of clinical outcomes. We anticipate we can recruit 200 patients by proactive outreach over 12 months. With 50 patients per group and 25% loss to follow-up we will have 81% power to detect a relative risk of self-reported ≥ 24 hour quit attempts of 1.8 for text messaging versus brief advice groups. We base this estimate on meta-analyses of smoking cessation text messaging trials, mostly from community settings or school-based settings, report a relative risk of 1.4 for 7-day point prevalence abstinence and 1.6 for prolonged abstinence measured at six-months.^{8,71}

Hypothesis 2: A 12 week text messaging intervention providing personalized, tailored behavioral support and advice about using nicotine replacement therapy (NRT) plus 2 weeks of NRT mailed to the participant will increase adherence to NRT compared to subjects receiving only 2 weeks of NRT as measured by duration of NRT use in days.

For our secondary outcome of medication adherence, we estimate patients randomized to the NRT will use a mean 9 days of medication based on the offer to mail them 2 weeks of medication for free.⁷² With this sample size, we also have 80% power to detect an increase in days of NRT use from 9 to 12 days in NRT vs. NRT+TM.

Hypothesis 3: A 12 week text messaging intervention will increase the rate of *biochemically confirmed* past 7-day point prevalent tobacco abstinence at end of treatment compared to subjects receiving no text messaging intervention.

We do not expect to have power to detect cessation in this pilot study. With 100 subjects and 25% loss to follow-up we will have 80% power to detect an increase from 6% among the BA & NRT groups to 22% in TM & TM + NRT groups.

Regardless, this pilot study aims to generate an estimate of effect size on cessation at 12 weeks for further studies.

Hypothesis 4: A 12 week text messaging intervention will increase the number of days not smoking compared to subjects receiving no text messaging intervention.

Assuming $\alpha=0.05$ and 25% loss to follow-up, leaving 75 patients, we have 68% power to detect an increase in days not smoked from 0.2 in groups receiving no text messaging (BA & NRT) to 1 in groups receiving text messaging (TM & TM + NRT) assuming a standard deviation of 2.

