Hypothesis 5: A 12 week text messaging intervention will decrease number of cigarettes smoking compared to subjects receiving no text messaging intervention.

Assuming $\alpha=0.05$ and 25% loss to follow-up, leaving 75 patients, we have 75% power to detect a decrease in cigarettes smoked per day from 15 among those receiving no text messaging (BA & NRT) to 12 in groups receiving text messaging (TM & TM + NRT) assuming a standard deviation of 7.

VII. RISKS AND DISCOMFORTS

- a. Complications of surgical and non-surgical procedures
Not applicable

- b. Drug side effects and toxicities

Side effects of the nicotine patch may include itching, burning or tingling when the patch is applied. This usually goes away within an hour, and is a result of nicotine coming in contact with the skin; redness or swelling at the patch site for up to 24 hours; dizziness; headache; upset stomach; vomiting; diarrhea; and palpitations.

Side effects of the nicotine lozenge include mouth irritation or ulcers, in addition to nicotine-related side effects of dizziness; headache; upset stomach; vomiting; diarrhea, and palpitations.

- c. Device complications/malfunctions

Errors in the text messaging platform include skipped text messages or failure to respond to a user-initiated text message. While this may affect the fidelity and clarity of the text messaging intervention we do not think this poses a risk to subject health or well-being.

- d. Psychosocial (non-medical) risks

i). Psychological discomfort: Quitting smoking can be psychologically stressful and, at times, physically uncomfortable because of cravings and nicotine withdrawal symptoms.

ii). Risks to privacy: Text messages are not a secure messaging platform. Any person using the subject's designated phone can see the messages which may include information about quitting

smoking. It may be psychologically stressful for subjects if other persons see text messages disclosing their smoking status. We will also collect and record identifying information (e.g. name, date of birth and social security number) and ask about potentially sensitive topics (smoking history, depression screening questions, anxiety screening questions, alcohol and substance use disorder screening questions). Name, telephone number, and smoking status will be shared with the text messaging vendor. The vendor underwent risk assessment by Research Information Security to evaluate their data security practices.

- e. Radiation risks
Not Applicable

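### The primary test omits readiness to quit, a randomization stratum, and lets a p<0.05 baseline test choose covariates; cigarettes per day is by default compared without its baseline value

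*Combined protocol and SAP*

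**What the plan says.** - **Randomization** (IV.c): "We will stratify by practice and readiness to quit in the next 30 days", with variable blocks and equal allocation to four arms.
- **Primary analysis** (VI, Data analysis): "comparing the primary outcome using chi-square analysis or multiple logistic regression analysis if any baseline factor is significantly imbalanced by group". The threshold is p<0.05, and the imbalanced factors become the independent variables. Baseline characteristics from the health record and the interview are compared across all four arms. Neither stratification factor is named as a covariate.
- **Contrast:** text messaging is tested on pooled arms if no interaction with NRT is found. Otherwise, "If interaction is present, we will compare the TM arm to BA for our primary analysis".
- **Readiness** enters only through additional "stratified analyses of the primary outcome, 7 day PPA, treatment use and days not smoked by readiness to quit".
- **Cigarettes per day** is a secondary outcome, under the same kind of rule: "cigarettes per day using chi-square or t-tests or logistic or linear regression if groups are imbalanced". Its baseline value comes with the Fagerstrom test (V.d), which "includes time to first cigarette after waking and cigarettes smoked per day".

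**The concern.** Stratified blocks make the arms nearly equal on readiness, so a test for imbalance is the wrong way to decide whether to adjust for it. Adjustment is useful because a covariate predicts the outcome, not because it differs between arms. Readiness is a plausible predictor here: the stratum is planning to quit within 30 days and the outcome is a quit attempt within 12 weeks.

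Under randomization, the factors that pass a p<0.05 screen do so by chance. The trial's own baseline draw then decides whether the primary result is a crude comparison or an odds ratio conditional on covariates nobody named beforehand. The screen also runs across four arms, whereas the primary contrast is between two groups (pooled, or TM against BA).

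At stake are some power and a stable definition of the effect, in a pilot whose stated purpose includes supplying an effect estimate for later studies.

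**Working it through.** **Inputs from the protocol.** Hypothesis 5: means 15 and 12, SD 7, 75 evaluable per pooled group, α 0.05, stated power 75%. Hypothesis 1: relative risk 1.8, 50 per group, 25% loss, stated power 81%, no control rate. Pilot mix (I.b): 68% ready, 32% not ready.

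**Assumed, because the protocol gives no figure.** Quit-attempt rates by readiness, the correlation r between baseline and 12-week cigarettes per day, and the number of baseline factors tested.

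**1. Reproduce the plan's Hypothesis 5 figure.** Power = Φ[δ/(SD·√(2/n)) − 1.96] = Φ[3/(7·√(2/75)) − 1.96] = Φ(2.624 − 1.960) = 74.7%; the noncentral t gives 74.1%. The stated 75% is therefore an unadjusted comparison.

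**2. Add the baseline value.** The residual SD becomes 7·√(1 − r²).

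| r | residual SD | power (normal) | power (noncentral t) |
|---|---|---|---|
| 0.3 | 6.68 | 78.6% | 78% |
| 0.5 | 6.06 | 85.8% | 85% |
| 0.7 | 5.00 | 95.7% | 95% |

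The imbalance rule recovers little of this. In 20,000 simulated trials, adjusting only when baseline differed between the pooled groups at p<0.05 gave 75.4% against 85.1% for routine adjustment at r = 0.5, and 76.5% against 95.4% at r = 0.7. Its size was 4.1% and 3.7%.

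**3. Would the rule select readiness?** With permuted blocks of 4 or 8 within practice and readiness, and 5, 10 or 15 practices, a four-group test at 0.05 selected it in 0 of 12,000 simulated trials. Without stratification it did so in 4.8%.

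**4. How often would something else trigger the switch?** For k independent factors, 1 − 0.95^k gives 40% (k = 10), 54% (k = 15) and 72% (k = 25). Correlated factors would lower this.

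**5. Primary outcome: chi-square against a readiness-stratified Mantel-Haenszel test.** Assume 68% ready and a common odds ratio of 2.5. At 50%/20% the control rate is 0.68×0.50 + 0.32×0.20 = 40.4% and the treated rate is 0.68×0.714 + 0.32×0.385 = 60.9%, a relative risk of about 1.5. Sizes are for the chi-square; powers are chi-square against stratified.

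| Control rates, ready / not ready | 75 fixed per pooled arm | 25% random loss from 100 |
|---|---|---|
| 40% / 40% | size 5.5–5.7%; power 80.7% vs 79.0% | size about 5%; power about 79% for both |
| 50% / 30% | size 5.2%; 78.1% vs 78.5% | size 4.7%; 76% vs 77% |
| 50% / 20% | size 4.5%; gain 2 points | size 4.5%; 72% vs 75% |
| 60% / 20% | size 4.0%; 67.9% vs 71.5% | size 3.9%; 65% vs 71% |

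With random loss the stratified test held its size at 4.9–5.1%. For TM against BA alone at the same odds ratio, power is 44% vs 47% (50%/20%) and 38% vs 44% (60%/20%).

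**6. The plan's own effect size.** The sample-size text specifies "quit attempts of 1.8 for text messaging versus brief advice groups". With 50×0.75 = 37.5 per arm, a control rate of 40% (treated 1.8×40% = 72%) gives 81%. Stratum rates averaging about 40% are 45%/30% (0.306 + 0.096 = 40.2%) and 50%/20% (40.4%). Solving for a relative risk of 1.8 gives odds ratios of 4.01 and 4.54. TM vs BA power is then 82% vs 82% and 83% vs 85%. For the pooled contrast both tests reach 98–99%.

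**7. The written rule as a whole.** With 15 non-prognostic candidate factors and an odds ratio of 2.5:

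| Control rates | size of rule | power of rule | power, readiness pre-specified |
|---|---|---|---|
| 50% / 30% | 4.5% | 75% | 76% |
| 50% / 20% | 4.6% | 72% | 76% |
| 60% / 20% | 4.0% | 65% | 71% |

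The switch occurred in 52–54% of trials.

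**The case against.** The strongest case against is that little is lost on the primary outcome. At the plan's relative risk of 1.8 the gain is 0 to 2 points, and nil for the pooled contrast. The larger gains need a smaller effect and assumed stratum rates. The trigger does no measurable harm to size, and its power is within about 1 to 2 points of never adjusting. That simulation made every candidate factor non-prognostic, whereas the real list includes dependence, past quit attempts and motivation. If readiness does not predict quit attempts, stratifying costs up to 1.7 points with fixed arm sizes and 0.2 to 0.3 with random loss. The cigarettes-per-day gain concerns one secondary outcome and depends on an assumed correlation; the protocol does not say whether the baseline value is a count or a category, and the regression option could admit it if imbalanced. A valid, slightly conservative test may be thought adequate for a pilot.

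All of this stands as a limit on size. It does not justify the rule. The analyses by readiness leave the primary test unadjusted, and the trigger still lets chance choose the model. A small trial has most use for precision already paid for at randomization and baseline.

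**Conclusion.** The concern holds, as a worthwhile improvement rather than a validity error. The primary model is not fixed in advance, the selection rule effectively excludes the one covariate the design itself treats as important, and the default analysis of cigarettes per day discards available precision.

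False-positive risk is not materially raised. The chi-square is conservative when readiness is clearly prognostic (size 3.9–4.5%) and close to nominal otherwise. The primary-outcome loss ranges from nothing to about 6 points, depending on assumed stratum rates and effect size, and is near zero at the plan's own relative risk. The clearest gain is for cigarettes per day, 4 to 21 points over the unadjusted 74%, if the correlation with baseline is between 0.3 and 0.7.

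**What to change.** In VI, Data analysis:

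- Delete the p<0.05 imbalance trigger for all outcomes.
- Pre-specify readiness (ready / not ready) as a covariate in logistic regression, or as the Mantel-Haenszel stratum, for the primary and other binary outcomes. Apply this in both branches: the pooled factorial comparison, with NRT assignment in the model, and TM against BA.
- Include practice, collapsed or as a random effect, if numbers allow.
- Analyse 12-week cigarettes per day by linear regression on treatment, baseline cigarettes per day and readiness. Confirm that the baseline value is recorded as a count.
- Keep the readiness-stratified analyses as secondary.
- Report a standardized risk difference or relative risk beside the odds ratio, which becomes conditional on readiness.

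The cost is a few sentences, with no new data or patients. If readiness proves non-prognostic, the price is the small loss of power noted above.
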